A cohort of consecutive patients (diabetics vs. non-diabetics) with IDCM and NYHA class III/IV heart failure refractory to maximum medical therapy and treated with cardiac transplantation at the Division of Cardiac Surgery of the University of Campania "Luigi Vanvitelli" will be evaluated prospectively. At the Department of Medical Sciences will be conducted the clinical follow-up for cardiometabolic evaluation (eg routine, glycemic compensation). The molecular and cellular study will be conducted at the department of biochemistry. The follow-up will be 12 months. Patients will be recruited aged > 18, <75 years, with indication to receive a heart transplant (survival score for accepted heart failure (HFSS) at high risk, peak VO₂ <10 ml / kg / min after reaching the anaerobic threshold; recurrent symptomatic ventricular arrhythmias refractory to medical treatment, ICD and surgical), affected by IDCM with heart failure in class III / IV NYHA refractory to maximal medical therapy; diabetic and non-diabetic patients. Patients with non idiopathic dilated heart disease (valvular disease, ischemic-infarct heart disease, etc.) will be excluded. All patients will be included in the study after signing the informed consent to participate in the study. The study will be performed according to the Helsinki Declaration.

Explanted heart analysis

Myocardial tissues from hearts removed from diabetics vs. non-diabetics will be analyzed from a histological, microscopic and metabolic functional point of view. From the residual portion of the heart removed, after routine histological analyses conducted according to the "Heart Transplant Clinical Guidelines 2017". (9), a portion of muscle tissue (quantity 5-10 mm³) will be removed, from which 3 portions will be obtained: one portion will be incorporated into the OCT compound for immunohistochemical analysis, a second portion will be immediately frozen in liquid nitrogen and stored at -70°C for WB evaluation, and a third portion will be used for quantitative evaluations performed by ELISA.

Endo-myocardial biopsies and Follow up

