Transplanted patients will be followed through an echocardiographic evaluation (enrolment and 3-6-12 months follow-up), to evaluate cardiac functional parameters, metabolic parameters and survival outcomes (death for all causes, cardiac death, re-hospitalisation for heart failure). In all transplanted patients endo-myocardial biopsies (EMB) are collected according to normal clinical practice by the "ASHI" guideline (9): weekly for the first month; every 2 weeks for the following month; 1 for the following 4 weeks; 1 for the following 6 weeks; every 3 months for the following 2 years; and finally every 6 months for the following 3 years. 2-6 (usually 4, 1 to 3 mm³) fragments of myocardial tissue will be collected from the apical segment of the right side of the interventricular septum (IVS). The collected myocardial tissue will be immediately analyzed for histopathological evaluation of rejection. From the remaining portion of tissue 3 portions will be obtained: one portion will be incorporated into the OCT compound for immunohistochemical analysis, a second portion will be frozen immediately in liquid nitrogen and stored at -70°C for PCR evaluation, and a third portion will be used for quantitative evaluations performed by ELISA. The conservation and morpho-functional evaluation of biopsy samples will be carried out at the Bio-Bank of the University of Campania "Luigi Vanvitelli".

Biopsies analysis

PCR.

Total RNA will be isolated from human heart sample homogenates using the RNeasy Mini kit (74106, Qiagen), according to the manufacturer's protocols "Stabilization of RNA in collected animal tissues" and "Purification of total RNA from animal tissues". RNA concentration and purity will be determined using the NanoDrop 2000c (Thermo Fisher Scientific) spectrophotometer. Genomic DNA (gDNA) contamination will be removed from RNA samples prior to the Reverse Transcription (RT) phase, performed on the Gene AMP PCR System 9700 (Applied Biosystems)

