Study population groups (diabetics vs. non-diabetics) will be compared using the Pearson test for categorical variables and the Kruskal-Wallis test for continuous variables. Candidates for admission to the multivariate model will be identified by focusing on factors that will differ significantly (P value < 0.05) in the univariate analysis among diabetic vs non-diabetic patients. Cox regression will be used to construct the predictive model of mortality. The risk ratio for mortality will be adjusted by age, BMI, cholesterol, LDL, triglycerides and aspirin, ticlopidine, anti-aggregants, beta-blockers, ACE inhibitors or tailors, antidiabetic drugs, statins, etc. present at the time of admission to hospital for cardiac transplantation. The analysis of survival after cardiac transplantation will be performed using the Kaplan-Meier curve and the Cox regression method. Mortality curves will be obtained separately for diabetic and non-diabetic patients, and then compared using the log-rank test. All tests will be considered significant if they have a value of $p < 0.05$. All tests will be conducted in 2 populations: diabetic vs non-diabetic patients after cardiac transplantation. The SPSS program (version 21, IBM SPSS) will be used for all analyses.

References

2. L López-Sainz Á, Barge-Caballero E, Barge-Caballero G, Couto-Mallón D, Paniagua-Martin MJ, Seoane-Quiroga L, Iglesias-Gil C, Herrera-Noreña JM, Cuenca-Castillo JJ, Vázquez-Rodríguez JM, Crespo-Leiro MG. Late graft failure in heart transplant recipients: incidence, risk factors and clinical outcomes. *Eur J Heart Fail.* 2018;20:385-394.

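### The mortality Cox model has at least 13 partly redundant terms and no planned number of deaths; below about 65 to 130 deaths its diabetes hazard ratio is likely to be unstable and its prediction over-optimistic

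*Combined protocol and SAP*

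**What the plan says.** The Statistical analysis section gives the purpose of the model: "Cox regression will be used to construct the predictive model of mortality". The mortality risk ratio is to be "adjusted by age, BMI, cholesterol, LDL, triglycerides and aspirin, ticlopidine, anti-aggregants, beta-blockers, ACE inhibitors or tailors, antidiabetic drugs, statins, etc", using values at admission for transplantation.

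The same section gives a second rule: "Candidates for admission to the multivariate model will be identified by focusing on factors that will differ significantly (P value < 0.05" in the univariate comparison of diabetic and non-diabetic patients. It does not say how this screen combines with the named list. It also plans Kaplan-Meier curves by diabetes status with a log-rank test.

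The Patients section describes the cohort as "A cohort of consecutive patients (diabetics vs. non-diabetics) with IDCM and NYHA class III/IV heart failure refractory to maximum medical therapy", "treated with cardiac transplantation at the Division of Cardiac Surgery of the University of Campania". It is narrowed further: "Patients with non idiopathic dilated heart disease (valvular disease, ischemic-infarct heart disease, etc.) will be excluded". Death is one of the "survival outcomes (death for all causes, cardiac death, re-hospitalisation for heart failure" in the section on biopsies and follow-up. Follow-up is 12 to 36 months under Study protocol but 12 months under Patients.

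The document states no sample size, accrual period, expected deaths, mortality rate, limit on model terms, shrinkage or internal validation.

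**The concern.** A Cox model draws its information from deaths, not from patients. A long covariate list with an open end, fitted to one centre's transplants for one cause of heart failure, can easily have only one to four deaths per term. Two outputs are then at risk. The adjusted diabetes hazard ratio may have no finite estimate, or may be far from the truth by chance. The predictive model may appear to separate survivors from deaths when none of its terms predicts anything. Redundant covariates make both worse, above all one that almost restates the exposure. Sex and the severity measures used at entry (HFSS, peak VO₂, NYHA class) are not named as adjusters, so the list is long without covering severity.

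**Working it through.** The plan states no figure to reproduce, so the check asks what the stated list would require.

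**1. Terms.** Named adjusters: age, BMI, cholesterol, LDL, triglycerides (5); aspirin, ticlopidine, anti-aggregants, beta-blockers, ACE inhibitors or the unclear alternative beside them (counted as one), antidiabetic drugs, statins (7). 5 + 7 = 12. With diabetes this is 13, before anything the open end adds.

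**2. Deaths and patients needed.** Deaths = terms × deaths per term: 13 × 5 = 65 and 13 × 10 = 130. Patients = deaths / mortality, with mortality assumed at 10% to 30%:
- 65 deaths: 65/0.30 = 217 to 65/0.10 = 650 patients.
- 130 deaths: 130/0.30 = 434 to 130/0.10 = 1,300 patients.

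**3. Deaths per term at assumed cohort sizes** (N × mortality / 13). N = 161 is the size in the title of a cited ten-year review from another centre, and is used only for scale.

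| N | 10% mortality | 30% mortality |
|---|---|---|
| 50 | 0.4 | 1.2 |
| 100 | 0.8 | 2.3 |
| 161 | 1.2 | 3.7 |
| 200 | 1.5 | 4.6 |
| 300 | 2.3 | 6.9 |

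Up to N = 200, the ratio stays below 5 throughout the assumed range.

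**4. Diabetes against antidiabetic drugs.** Let p be the share diabetic and q the share of diabetics on drug, with no non-diabetic on drug. The squared correlation is q(1−p)/(1−pq), and the variance inflation is 1/(1 − that value).
- p = 0.75 (the Background figure for diabetes in idiopathic disease), q = 0.90 assumed: 0.225/0.325 = 0.692, inflation 3.25.
- p = 0.30 assumed, q = 0.90: 0.63/0.73 = 0.863, inflation 7.3.
- Over q = 0.70 to 0.95, inflation runs from 1.6 to 5.7 at p = 0.75 and from 2.6 to 14.3 at p = 0.30.

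As an illustration, Schoenfeld's formula (two-sided 0.05, 80% power and hazard ratio 2, all assumed; 75:25 split) gives 88 deaths. With the drug term this becomes 88 × 3.25 = 286.

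**5. Null simulations.** Every true hazard ratio is 1. Assumptions: 15% mortality, 30% to 40% diabetic, 30 to 400 runs per cell. Covariate distributions are also assumed, so these results are illustrative.
- Apparent c-index (true value 0.50), 12 or 13 terms: 0.85 to 0.86 at N = 50, 0.74 to 0.76 at N = 100, 0.69 at N = 161, 0.67 to 0.68 at N = 200, and 0.59 at N = 867 (867 × 0.15 = 130 deaths).
- Fitted diabetes hazard ratio wrong by more than 4-fold, antidiabetic term included: 66% to 79% of runs at N = 100, 40% to 48% at N = 161, none at N = 867. Without that term, 9% at N = 100.
- Type I error for diabetes, 12 terms without antidiabetic drugs, at N = 50, 100 and 200: likelihood-ratio test 17.5% to 19%, 9.3% to 11.5% and 3.7% to 7%; Wald test 3.0% to 5%, 4.3% and 3.0%.

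**The case against.** The strongest objection is that the document gives no sample size, accrual period or mortality, so nobody can say that deaths will be few. This stands. A reader might infer that the hazard ratio and the model are bound to be artefacts of overfitting, but the document does not support that. The conclusion has to be conditional on the deaths observed, and follow-up of up to 36 months would raise the count.

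A reader might also infer that the test of diabetes will reject too often. That appears mainly with a likelihood-ratio test, which the plan does not specify, at around 7 deaths (50 × 0.15 = 7.5). Wald tests show no inflation, and by N = 200 the likelihood-ratio excess is small or absent. Inflated type I error should not be claimed more widely.

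The share of fits without a stable solution depends heavily on assumed drug use. At N = 100 and 15% mortality it was 23% with one drug at 10% and another at 80%, but 1% with every drug at 40% to 50%. No single percentage should be relied on.

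The P < 0.05 screen might reduce the number of terms. But the named list is stated outright, and the screen selects on the diabetes contrast rather than on death and sets no cap. It does not remove the problem.

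Finally, the main aim is cellular, and overfitting does not touch the Kaplan-Meier and log-rank comparison. Both are true, but the adjusted risk ratio and the predictive model are separate planned outputs.

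**Conclusion.** The concern holds in conditional form. What follows from the text alone is the count of at least 13 terms, the overlap among them, and the absence of any death budget, cap, penalisation or validation. What rests on assumption is how far the deaths will fall short. At 5 to 10 deaths per term the requirement is 65 to 130 deaths. A single-centre, idiopathic-only cohort that does not reach this is likely to give an unstable adjusted diabetes hazard ratio and a predictive model that overstates its discrimination. The damage to the hazard ratio comes at least as much from the antidiabetic-drug term as from the number of terms. The sponsor should change this before the mortality analysis is run.

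**What to change.** State the expected number of patients and deaths. Replace the list and its open end with a short pre-specified set in a fixed order:
1. Diabetes and age, always.
2. Sex, then one baseline severity measure that varies within the cohort, such as continuous HFSS or peak VO₂. NYHA class is already restricted to III/IV by entry.
3. At most one antiplatelet term in place of three, and one lipid term in place of three.

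Add terms beyond the first two only as total deaths allow, counted without reference to diabetes group. At 10 deaths per term, for example, a third term enters at 30 deaths and a fourth at 40. Below 20 deaths the two-term minimum still applies, although it falls short of 10 per term. State that this set governs and that the P < 0.05 screen adds nothing to it.

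Leave antidiabetic drugs out of the model that estimates the diabetes effect. Use Firth-penalised Cox regression with profile-likelihood intervals when deaths are few. Report a bootstrap optimism-corrected c-index for any predictive model.

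Cost: SAP wording and software beyond the named SPSS version. BMI, beta-blockers, ACE inhibitors and statins would no longer be adjusted for, and reported discrimination will be lower.

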Unique Protocol ID: DCM-AHEAD

**Brief Title: Diabetes and Lipid Accumulationand Heart Transplant
(DCM-AHEAD)**

Official Title: Lipid Accumulation in Heart Transplant From Non-diabetic Donors to Diabetic Recipients

Project manager: [name]

Department of Advanced Medical and Surgical Sciences

[contact]

e-mail: [contact]

clinical trial number: NCT03546062

clinical trial registry: clinicaltrialgov.com

Naples November 19, 2019

BACKGROUND

[figure not shown]
Idiopathic dilated cardiomyopathy (IDC) is defined by the presence of left ventricular systolic dysfunction in the absence of an abnormal loading condition or significant coronary heart disease (1). IDC is the leading cause of end-stage heart failure (HF) and is responsible for half of all heart transplants (HTx) (1). Endocrine disorders, including diabetes, are known to be associated with IDCs. Diabetes mellitus (DM), which is present in 75% of patients with idiopathic IDC, is an independent risk factor for the development of heart failure and death in IDC (2-4). Therefore, DM may exacerbate the need for HTx; moreover, diabetic patients are less suitable for HTx and DM remains an independent risk factor for death even after HTx (5). Recent studies have revealed the presence of diabetic cardiomyopathy, a condition of myocardial dysfunction without coronary heart disease (6, 7). This term was first introduced by Rubler et al. (8) in 1972, which highlighted patients with diabetes and congestive heart failure with normal coronary arteries. The pathophysiological mechanisms by which diabetes affects the development and progression of diabetic heart disease are not known. Therefore, the aim of our study will be to evaluate, in the diabetic heart removed, the presence of any cellular alterations related to diabetic disease. In addition, the progression of such lesions in the transplanted heart in diabetic patients will be evaluated.

MATERIALS AND METHODS

Study protocol

A prospective observational study will be conducted with a follow-up duration ranging from a minimum of 12 months to a maximum of 36 months (Figure).

STUDY PROTOCOL

Patients

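### If diabetes status is the Cox exposure and practically only diabetics take antidiabetic drugs, a yes/no drug adjuster makes the diabetes risk ratio compare untreated diabetics, not all diabetics, with non-diabetics

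*Combined protocol and SAP*

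**What the plan says.** All of this is in the Statistical analysis section of the combined protocol and SAP, except where noted.

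- Model: "Cox regression will be used to construct the predictive model of mortality".
- Adjusters: "The risk ratio for mortality will be adjusted by age, BMI, cholesterol, LDL, triglycerides and aspirin, ticlopidine, anti-aggregants", continuing with "beta-blockers, ACE inhibitors or tailors, antidiabetic drugs, statins, etc. present at the time of admission to hospital for cardiac transplantation". The drug variable is therefore a baseline one. Its coding (yes/no, class or other) is not given.
- Candidates for the multivariable model: "factors that will differ significantly (P value < 0.05) in the univariate analysis among diabetic vs non-diabetic patients".
- Unadjusted comparison: "Mortality curves will be obtained separately for diabetic and non-diabetic patients, and then compared using the log-rank test".
- Scope: "All tests will be conducted in 2 populations: diabetic vs non-diabetic patients after cardiac transplantation".
- The Background section gives the motivating claim that "DM remains an independent risk factor for death even after HTx".

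No sentence names diabetes status as a term in the Cox model. None removes the antidiabetic-drug term, restricts it to diabetics, or plans a fit without it.

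**The concern.** An adjusted risk ratio needs an exposure, and diabetic against non-diabetic is the only contrast in the plan. Antidiabetic treatment is largely a consequence of having diabetes, so it is not an ordinary confounder of that contrast: the covariate sits inside one level of the exposure. With both terms in the model, the diabetes coefficient no longer answers the question a reader would assume.

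In a partly treated cohort nothing in the fitted model flags this. A hazard ratio labelled diabetes would be reported, and it could be too low or too high for diabetics as a whole. A non-significant value could be read as showing that diabetes is not independently related to death after transplantation, when the model had tested something narrower. The adjusted Cox result is also the plan's only confounder-adjusted mortality analysis.

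**Working it through.** The plan states no sample size, event count, hazard ratio or power, so it has no figure of its own to reproduce. The check is algebra, followed by illustrations on assumed inputs.

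**1. What the coefficient means.** Let D = diabetes (0/1) and T = antidiabetic drug (0/1), with T = 1 only when D = 1. The occupied cells (D,T) are (0,0), (1,0) and (1,1). In h = h0·exp(bD·D + bT·T):
- bD = log HR, untreated diabetic vs non-diabetic
- bT = log HR, treated vs untreated diabetic
- bD + bT = log HR, treated diabetic vs non-diabetic

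If every diabetic is treated, D and T are the same column (rank 1 of 2) and bD cannot be estimated.

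**2. Precision.** With d0 and dD deaths in non-diabetics and diabetics, share q of diabetics treated, and equal risk in treated and untreated diabetics:

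SE multiplier = sqrt[(1/d0 + 1/((1−q)dD)) / (1/d0 + 1/dD)]

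- dD = d0, q = 50%: sqrt[(1 + 2)/2] = 1.22; q = 80%: sqrt[(1 + 5)/2] = 1.73
- dD = 4·d0, q = 50%: sqrt[(1 + 0.5)/1.25] = 1.10; q = 80%: sqrt[(1 + 1.25)/1.25] = 1.34

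Cox simulations agree (assumed N = 200, HR 2.0, hazard 0.16 per year, 1000 runs per setting). The 75% diabetic setting borrows the Background prevalence figure, which is not a cohort share. Study protocol gives follow-up as 12 to 36 months and Patients gives 12 months, so both were tried.

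| Setting | 50% treated | 80% treated |
|---|---|---|
| 40% diabetic, 12–36 months | 0.293/0.242 = 1.21 | 0.412/0.242 = 1.70 |
| 75% diabetic, 12–36 months | 0.322/0.30 = 1.07 | 0.386/0.30 = 1.29 |
| 40% diabetic, 12 months | 0.387/0.323 = 1.20 | 0.546/0.323 = 1.69 |
| 75% diabetic, 12 months | 1.07 | 1.27 |

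**3. Distortion.** Assume untreated diabetics have HR 1.2 and treated diabetics HR 2.0 against non-diabetics. The overall diabetes HR is roughly the share-weighted mean: 0.5×1.2 + 0.5×2.0 = 1.6 at 50% treated, and 0.2×1.2 + 0.8×2.0 = 1.84 at 80%. The adjusted coefficient stays near 1.2. With the risks reversed, the overall HR is about 1.6 and 1.36, while the coefficient is 2.0. With equal risk only precision is lost.

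Simulated fits for the first case (n = 20,000, equal groups, one further covariate, one fit per column, so some scatter):

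| Share treated | 50% | 70% | 80% | 90% | 95% |
|---|---|---|---|---|---|
| Diabetes HR, drug term left out | 1.56 | 1.72 | 1.92 | 1.90 | 1.95 |
| Diabetes HR, drug term in | 1.19 | 1.20 | 1.25 | 1.18 | 1.18 |
| Diabetes HR, treated diabetics deleted | 1.19 | 1.20 | 1.26 | 1.17 | 1.18 |

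The second and third rows match, as step 1 predicts.

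**4. Are the data lost?** No. In the 50% column the drug HR was 1.681, and 1.188 × 1.681 = 2.00, the assumed treated-vs-non-diabetic HR. The two yes/no terms and a three-level factor are the same model.

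**5. Does the P<0.05 screen keep the term out?** For a nested yes/no term, Pearson chi-square = N·q(1−p)/(1−pq), with p the share diabetic.
- 25 patients, 10 diabetic, 5 treated: 25 × 0.375 = 9.4, P = 0.002
- 20 patients, 15 diabetic, 8 treated: 20 × 0.222 = 4.4, P = 0.035
- 40 patients, 30 diabetic, 9 treated: 40 × 0.097 = 3.9, P = 0.049

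The tables are sparse: expected treated non-diabetics are 3, 2 and 2.25, and Fisher's exact P is 0.005, 0.055 and 0.081. The plan names a Pearson test, so drug use would usually qualify, but in very small cohorts only marginally.

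**6. If nesting is not perfect.** With 5% of non-diabetics on such a drug (6 of 120), the multipliers are about 1.15 at 50% and 1.5 at 80% treated, and the coefficient is no longer exactly the untreated contrast.

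**The case against.** The strongest reply is that the defect is conditional. It needs diabetes status as a Cox term, drug use practically confined to diabetics, and yes/no or exclusive-class coding, and the section states none of these. It calls the model predictive. The sentence on two populations could mean separate models per group. The adjuster list is open-ended and may be only illustrative. In a predictive or group-specific model there is no diabetes coefficient to misread. All of this stands as a limit on the claim. It does not remove it, because the plan does say that a risk ratio will be adjusted for these drugs and states neither alternative reading.

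Second, the yes/no model and the three-level factor have the same likelihood, so the loss of precision belongs to one coefficient and not to the study's information. This is right, and it places the harm in the reporting. It is also why no loss of power is claimed here.

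Third, every magnitude rests on assumed inputs. With N = 60, 40% diabetic, 12 months and the same hazards, one expects about 36×(1−e^−0.16) + 24×(1−e^−0.32) = 12 deaths, against 12 named adjusters. Such a model is unreliable with or without this term. That stands, and in a cohort that small the drug term would not be the main problem.

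Fourth, passing the screen makes a factor a candidate, and no later entry rule is given. That stands too: the screen fails to protect, but it does not force entry.

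**Conclusion.** The point holds in conditional form. Under the three conditions, the reported diabetes risk ratio would be that of untreated diabetics against non-diabetics. Its standard error would be about 1.1 to 1.2 times larger at 50% treated and 1.3 to 1.7 times at 80%. It would depart from the overall effect, in either direction, whenever treated and untreated diabetics differ in risk. It would not be estimable if all diabetics were treated. The algebra is exact; the sizes are illustrative.

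A reader might infer more than the documents support:
- That the plan definitely fits this model. The exposure and the coding are unstated. With several overlapping drug classes entered additively, the coefficient would instead be an extrapolation to a diabetic on no drug.
- That treated diabetics are discarded. They are not: the two coefficients together recover their contrast.
- That the mortality comparison as a whole is compromised. The Kaplan-Meier curves and log-rank test do not use the term.

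Severity is minor to moderate. Mortality is one of several follow-up outcomes, and the stated aim is cellular alterations in the explanted and transplanted heart.

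**What to change.** In the Statistical analysis section, state that diabetes status is the exposure of the between-group Cox model. Remove antidiabetic drugs from its adjusters, and say that neither the P<0.05 screen nor the open end of the list may bring them back.

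If drug use is of interest, either analyse it within diabetics only, or use one three-level factor (non-diabetic, diabetic without drugs, diabetic with drugs) and report each contrast under its own name. If a group-specific or purely predictive model was meant, say so and report no adjusted diabetes risk ratio from it.

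The cost is one or two lines of wording, with no new data, patients or visits. On the assumptions above (N = 200, 12–36 months, 50 to 95% treated), the three-level factor estimates diabetics with drugs vs non-diabetics with a standard error of 0.25–0.29 (40% diabetic) or 0.30–0.32 (75% diabetic). The overall diabetes effect has 0.24 and 0.30, so little precision is given up for that contrast.

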using the QuantiTect Reverse Transcription Kit (205311, Qiagen), according to the "Reverse Transcription with Elimination of Genomic DNA for Quantitative, Real-Time PCR" protocol. The final step for real-time PCR analysis (qPCR) will be performed on the CFX96 Real-time System C1000 Touch Thermal Cycler (BIORAD). The analysis will be performed according to the "Two-Step RT-PCR (Standard Protocol)" protocol, using the QuantiTect SYBR Green PCR Kit (204143, Qiagen) and specific QuantiTect Primer Assays (249900, Qiagen) for each gene tested. Relative quantization of gene expression will be performed using the $2^{-\Delta\Delta Ct}$ method, using GAPDH as the cleaning control gene. P values will be calculated on the basis of a student t-test or one-way variance analysis (ANOVA), followed by Dunnett's post hoc test; $P < 0.05$ will be considered significant.

Immunofluorescence. Confocal laser scanning microscopy.

The analysis of immunofluorescence in sections of the myocardium will be performed according to the manufacturing protocol using the laser scanning confocal microscope (LSM 700; Zeiss). In particular, the complete removal of the paraffin will be carried out before proceeding to the staining of the section. For this purpose, the slides will be deparaffinized by passing them through xylenes, alcohols and water. An antigen recovery buffer (10 mM sodium citrate, 0.05% Tween 20, pH 6.0) will be added to the dewaxed and rehydrated sections and boiled in the microwave for 20 minutes. After 20 minutes, immunofluorescence staining will be performed using specific antibodies against PPAR-alpha (1 μ g/ml) (polyclonal rabbit, NB600-636, Novusbio, Abingdon, UK), PPAR-gamma (1 μ g/ml) (mouse monoclonal, orb69095, Biorbyt, Cambridge, UK) or against SREBP1 (1 μ g/ml) (polyclonal rabbit, ab28481, Abcam, Cambridge, UK). Secondary antibodies will be conjugated with Alexa Fluor 633 or Alexa Fluor 488 (Life Technologies Italia, Monza, Italy). Nuclear contrast staining will be performed using the VECTASHIELD® mounting medium with DAPI (H-1200, Vector Laboratories, Burlingame, USA).

Immunohistochemistry.

Oil Red O (Solvent Red 27, Sudan Red 5B, C.I. 26125, C26H24N4O) will be used for the assessment of the accumulation of intramyocytic lipids.

Statistical analysis

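### Lesion progression in the grafts of diabetic recipients is a stated aim, but no specified analysis tests change over time in them or relates graft lipid to glycaemic control

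*Combined protocol and SAP*

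**What the plan says.** **Aim.** The Background, after the aim for the explanted heart, adds: "In addition, the progression of such lesions in the transplanted heart in diabetic patients will be evaluated".

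**Data.** The Patients section provides for "clinical follow-up for cardiometabolic evaluation (eg routine, glycemic compensation"; it names no glycaemic measure and no visit schedule for it. The section on endo-myocardial biopsies and follow-up gives "echocardiographic evaluation (enrolment and 3-6-12 months follow-up", lists metabolic parameters among the things followed, and has serial biopsies in all recipients, starting "weekly for the first month; every 2 weeks for the following month". Oil Red O is the stain for lipid within myocytes, and lipid accumulation is the subject of the official title.

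**Analysis.** The Statistical analysis section opens: "Study population groups (diabetics vs. non-diabetics) will be compared using the Pearson test for categorical variables and the Kruskal-Wallis test for continuous variables". It adds Kaplan-Meier curves with a log-rank test between the groups and a Cox model for mortality. It then states: "All tests will be conducted in 2 populations: diabetic vs non-diabetic patients after cardiac transplantation". Separately, the PCR paragraph gives gene expression a "student t-test or one-way variance analysis (ANOVA), followed by" Dunnett's post hoc test, without saying which groups or time points are compared.

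**The concern.** Progression is change over time in the same graft. A comparison of diabetic with non-diabetic recipients at an unspecified biopsy does not measure it. Read literally, the sentence on two populations also leaves no room for an analysis within diabetic recipients, so well-controlled and poorly controlled diabetic recipients count as the same exposure in every tissue comparison.

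At stake is a stated aim. With many biopsies per recipient and no model named, the choice of biopsy, of change measure and of how to handle repeated samples would be made after the data are seen. Any progression result would then be post hoc.

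**Working it through.** **1. Aim against analysis.** The plan states no sample size, power, effect size or SD, so there is no figure to reproduce. The first check is a reading of the listed analyses.

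| Specified analysis | Outcome | Tests change within diabetic recipients? | Uses glycaemic level? |
|---|---|---|---|
| Pearson, Kruskal-Wallis | Group characteristics and measures | No, between groups | No |
| Kaplan-Meier, log-rank | Mortality | No, between groups | No |
| Cox regression | Mortality | No | Not named; could enter through the P < 0.05 rule |
| t-test or one-way ANOVA with Dunnett | Gene expression | Groups and time not defined | Not named |

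No row covers graft lipid over time, or graft lipid against glycaemia.

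**2. Does the two-group test stand in for a progression test?** Assumed: difference 0.5 SD, two-sided 0.05, 80% power, so (1.960 + 0.842)² = 7.85.

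- Two groups at one time: n per group = 2 × 7.85 / 0.5² = 62.8, so 63.
- Paired change within diabetic recipients: n = 2(1 − ρ) × 7.85 / 0.5². For ρ = 0.3, 0.5, 0.7 this is 44, 32, 19.
- Difference in change between groups: twice the unrounded paired figure, per group: 88, 63, 38.

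The three questions have different requirements, so one does not replace another.

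**3. Is there a power argument for glycaemia?** Assumed: glycaemic measure 5.4 (SD 0.4) in non-diabetic and 7.5 (SD 1.2) in diabetic recipients, and glycaemia linearly explaining 20% of lipid variance. The share of glycaemic variance carried by the label is p(1 − p)d² / [p(1 − p)d² + p·1.2² + (1 − p)·0.4²], with d = 2.1 and p the proportion diabetic.

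- p = 0.5: 1.1025 / (1.1025 + 0.80) = 58%
- p = 0.3: 0.9261 / (0.9261 + 0.544) = 63%
- p = 0.7: 0.9261 / (0.9261 + 1.056) = 47%

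Simulated power with equal groups:

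| Total n | Kruskal-Wallis on label | Glycaemia, all patients, no label | Glycaemia within diabetic recipients | Glycaemia, all patients, label in model |
|---|---|---|---|---|
| 30 | 46% | 75% | 33% | 38% |
| 40 | 58% | 85% | 42% | 48% |
| 60 | 76% | 96% | 62% | 68% |

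Repeat runs agreed within about three points. Only the regression without the label beats Kruskal-Wallis, and that regression mixes the diabetes contrast with the gradient. The two that isolate glycaemic level have less power.

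**4. Why repeated biopsies need their own model.** Reading the schedule as four weekly biopsies, two in the next month, then one and one gives 4 + 2 + 1 + 1 = 8 per recipient before the three-monthly phase. If these are treated as independent when testing a per-patient exposure, the variance is understated by 1 + 7ρ. At ρ = 0.3 this is 3.1, and the true size of a nominal 5% test is 2P(Z > 1.96/√3.1) = 27%. At ρ = 0.5 it is 4.5 and 36%. Simulation gave 25–35% over the same range.

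**The case against.** The strongest reply is that diabetic v non-diabetic is the declared cohort design, so a two-group contrast is not an error. That stands, and the two-group test should stay. It does not cover the progression aim, which the plan adds itself.

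A reader might infer that every test is a bare yes/no contrast and that glycaemic information is discarded. The documents do not support that. The Cox model is multivariable, and its entry rule could admit a glycaemic variable. However, its outcome is mortality and its listed covariates are those present at admission. One-way ANOVA with Dunnett can handle more than two groups, but here it is for gene expression, defines neither groups nor time, and assumes independent observations, which serial biopsies from one recipient are not.

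A reader might also infer that continuous glycaemia would recover lost power. The third step of the working shows that this fails for the analyses that isolate glycaemic level. If lipid depends only on diabetes status, there is no gradient to find.

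Nor is a gradient within diabetic recipients free of confounding. It removes differences between diabetic and non-diabetic recipients as an explanation, but BMI, triglycerides, statins and antidiabetic drugs, all in the plan's adjustment list, can vary with glycaemia among diabetic recipients.

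Finally, the data may not all be in hand. No glycaemic measure is named, none is tied to the biopsy dates, and no quantitative Oil Red O scale is given. This adds to the cost but does not remove the gap.

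**Conclusion.** The point holds in this form: progression in the grafts of diabetic recipients is a stated aim with serial tissue to address it, and no specified analysis tests change over time in those recipients or relates graft lipid to glycaemic control. The missing longitudinal test is the stronger half and follows from the text alone. The glycaemia half is an improvement worth making because it asks something the diabetes label cannot answer; it is not a gain in power.

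The size of the loss cannot be given. All sample sizes, powers and false-positive rates above rest on assumed inputs and serve only to show that the questions differ and that repeated biopsies cannot be treated as independent. The plan should be amended; the two-group comparisons are unaffected.

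**What to change.** Keep the two-group test and amend the sentence on two populations to add one pre-specified secondary analysis:

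- **Model.** A mixed model for graft Oil Red O lipid across serial biopsies, with a patient random effect, time, group and group-by-time. Define the quantitative lipid scale and the biopsies included.
- **Reporting.** Give the time effect within diabetic recipients with a confidence interval, since this answers the aim. Report group-by-time beside it, to show whether the change differs from that in non-diabetic recipients.
- **One exploratory term.** Within diabetic recipients, add a named glycaemic measure as a continuous, time-updated exposure, adjusted for key covariates from the plan's own list as far as numbers allow. State how each value is matched to a biopsy.

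Restrict this to the one marker in the title. The cost is an amendment to the analysis text, one extra secondary analysis on biopsies already planned, and the naming of a glycaemic measure and its timing.
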